7.7.3. Adverse Event Documentation

All adverse events must be fully recorded on the Adverse Event Page via the Electronic Data Capture (EDC) system. Documentation must be supported by an entry in the subject file. Laboratory test, vital signs and ECG abnormalities considered by the Investigator to be clinically relevant should be reported on the Adverse Event page of the eCRF. Signs and symptoms of each AE should be described in detail (e.g., start and stop dates, severity/intensity, relationship to investigational product, action taken, and outcome).

Adverse events and laboratory test abnormalities fulfilling the definition of a serious adverse event should, in addition, be reported on the Serious Adverse Event Reporting Form.

7.7.4. Reporting of Serious Adverse Events

Study site personnel must alert Eli Lilly or its designee of any SAE within 24 hours of their awareness of the event via a sponsor-approved method. Alerts issued via telephone are to be immediately followed with official notification on study-specific SAE forms.

Serious adverse events occurring after a subject receive a dose of investigational product will be collected until 48 hours after the dosing of the investigational product, regardless of the investigator's opinion of causation. Therefore, SAEs that occur later than 48 hours after the dosing of the investigational product are not required to be reported unless the investigator feels the events were related to either investigational product or a protocol procedure.

If a patient experiences an SAE after signing informed consent, but prior to receiving investigational product, the event will NOT be reported unless the investigator feels the event may have been caused by a protocol procedure. Previously planned (prior to signing the ICF) surgeries should not be reported as SAEs unless the underlying medical condition has worsened during the course of the study.

8. STATISTICAL ANALYSIS

8.1. General Statistical Considerations

All statistical analyses will be performed using SAS® version 8.2 or higher.

Data will be summarized using descriptive statistics (number of subjects [N], mean, standard deviation [SD], median, quartiles, minimum, and maximum) for continuous variables and using frequency count and percentage for discrete variables. The demographic and baseline characteristics data will be summarized according to clinical group (healthy volunteers and subjects with cognitive impairment) at recruitment for all subjects in the safety population. Safety data will be summarized for all patients.

Subject listings of all data from the electronic case report forms (eCRFs) as well as any derived variables will be presented.

Additional details concerning statistical analyses will be included in the Statistical Analysis Plan (SAP).

8.1.1. Sample Size Estimation

This study is estimated to enroll about 100 subjects from A05 confirmatory arm. Current analyses with A05 exploratory arm data showed that for subjects met A05 confirmatory arm enrollment criteria (MCI or demented, MMSE between 20 and 27), AV1451 SUVR on average changed 0.0527 (SD=0.0970) for amyloid positive subjects at 9 months follow up. Assume a similar amyloid positivity to A05 exploratory arm (~60%), and assume the change of AV1451 SUVR is linear, this study is expected to have approximately 60 amyloid positive subjects and the mean change of AV1451 SUVR is expected to be 0.105, with a 95% confidence interval (0.0635, 0.1473).

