5.3. Selection of Subjects**5.3.1. Inclusion Criteria**

Subjects who meet all of the following criteria are eligible to enroll in this trial:

1. Subjects who participated as a confirmatory subject in the ¹⁸F-AV-1451-A05 study;
2. Subjects who completed the ¹⁸F-AV-1451-A05 study;
3. Subjects who signed an IRB approved informed consent prior to any study procedures.

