3.4. Sample Size Justification

This study is estimated to enroll about 100 subjects from A05 confirmatory arm. Current analyses with A05 exploratory arm data showed that for subjects met A05 confirmatory arm enrollment criteria (MCI or demented, Mini Mental State Exam (MMSE) between 20 and 27), flortaucipir SUVR on average changed 0.0527 (SD=0.0970) for amyloid positive subjects at 9 months follow up. Assume a similar amyloid positivity to A05 exploratory arm (~60%), and assume the change of flortaucipir SUVR is linear, this study is expected to have approximately 60 amyloid positive subjects and the mean change of flortaucipir SUVR is expected to be 0.105, with a 95% confidence interval (0.0635, 0.1473).

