6.2. Definitions of Baseline and Follow-up

Baseline characteristics and demographics will be gathered from the AV-1451-A05 datasets for confirmatory cohort subjects who participated in AV-1451-A18. All other baseline data (i.e. electrocardiogram, and safety labs) will be reported from data collected from the AV-1451-A18 CRFs.

Efficacy analysis evaluating longitudinal change will require the use of the Baseline flortaucipir SUVr quantitation, and Baseline and 18 Month MMSE from the AV-1451-A05 datasets to calculate change.

Safety analysis involving change from baseline (CFB) calculations for vital signs will consider AV-45-A18 *Prior to Injection* values as baseline and *Prior to Discharge* as follow-up.

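### The interval (0.0635, 0.1473) printed as a 95% CI in the sample-size rationale matches a two-sided 90% CI; the 95% CI from the same inputs is (0.0553, 0.1555)

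*Protocol*

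**What the plan says.** Protocol 8.1.1 bases the planned size on data from the A05 exploratory arm. It reports that "AV1451 SUVR on average changed 0.0527 (SD=0.0970) for amyloid positive subjects at 9 months follow up". It then tells the reader to "assume the change of AV1451 SUVR is linear" and, taking about 100 enrolled subjects and roughly 60% amyloid positivity, states that "this study is expected to have approximately 60 amyloid positive subjects". From this it concludes that "the mean change of AV1451 SUVR is expected to be 0.105, with a 95% confidence interval (0.0635, 0.1473".

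SAP 3.4 carries the same inputs and conclusion, with only the tracer name changed: "the mean change of flortaucipir SUVR is expected to be 0.105, with a 95% confidence interval (0.0635, 0.1473".

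Neither section states the time point to which the change is extrapolated, the SD at that time point, or the formula for the interval. The nearest indication of the horizon is in SAP 6.2, where the efficacy analysis uses "Baseline and 18 Month MMSE from the AV-1451-A05 datasets to calculate change".

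**The concern.** The printed mean of 0.105 is twice the 9-month mean, so the extrapolation is evidently to 18 months. If each subject's change is linear, the SD doubles as well. On those inputs with 60 subjects, a 95% interval should be visibly wider than the one printed, whereas the printed limits coincide with a 90% interval. The likely slip is use of the 0.95 quantile of the t distribution, which leaves 5% in each tail, where a two-sided 95% interval needs the 0.975 quantile.

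Neither document contains a power calculation, so this interval is the whole quantitative case for the planned size. A reader who takes the label at face value will expect a more precise estimate in the amyloid-positive subjects than the inputs support. Someone who later compares an observed 95% interval with the planned one could conclude that the data were noisier than expected when they were not.

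**Working it through.** **Inputs** (Protocol 8.1.1, repeated in SAP 3.4)
- 9-month mean change in amyloid-positive subjects: 0.0527
- 9-month SD of change: 0.0970
- Amyloid-positive subjects: about 60 (100 × 0.60)
- Printed result: mean 0.105, limits 0.0635 and 0.1473, labelled 95%

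**Printed interval taken apart**
- Midpoint: (0.0635 + 0.1473)/2 = 0.1054 = 2 × 0.0527. The mean was doubled.
- Half-width: (0.1473 − 0.0635)/2 = 0.0419.

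**Reproducing the printed limits**, using mean ± t × SD/√n
- SD = 2 × 0.0970 = 0.194 (inferred; not printed)
- SE = 0.194/√60 = 0.02505
- 90%: t(0.95, 59) = 1.6711; half-width = 1.6711 × 0.02505 = 0.04185; limits 0.06355 and 0.14725, which are the printed 0.0635 and 0.1473.
- In reverse, 0.0419/0.02505 = 1.673 standard errors, which on 59 degrees of freedom is a confidence level of 90.0%.
- The match is specific to a t interval at n = 60. The normal quantile at 90% gives (0.0642, 0.1466); the 90% t interval at n = 59 is (0.0632, 0.1476) and at n = 61 is (0.0639, 0.1469).

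**The 95% interval on the same inputs**
- t(0.975, 59) = 2.0010; half-width = 2.0010 × 0.02505 = 0.0501
- Limits: 0.1054 − 0.0501 = 0.0553 and 0.1054 + 0.0501 = 0.1555
- Ratio of half-widths: 0.0419/0.0501 = 0.836, so the printed interval is about 16% narrower than its label requires.

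**Does any SD scaling make the label right at n = 60?**

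| SD at the horizon | 95% CI by t | 95% CI by normal quantile |
|---|---|---|
| 0.0970 (unscaled) | (0.0803, 0.1305) | (0.0809, 0.1299) |
| 0.0970 × √2 = 0.1372 | (0.0700, 0.1408) | (0.0707, 0.1401) |
| 0.0970 × 2 = 0.1940 | (0.0553, 0.1555) | (0.0563, 0.1545) |

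None gives (0.0635, 0.1473). For the printed limits to be a 95% t interval at n = 60, the SD would have to be 0.0419 × √60/2.0010 = 0.162, which is 1.67 × 0.0970 and appears in neither document.

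**Scale.** With SD 0.194, a 95% half-width of 0.0419 would take about 85 amyloid-positive subjects (half-width 0.0421 at n = 84, 0.0418 at n = 85). This conveys the size of the discrepancy and is not a request for more subjects.

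**The case against.** The strongest objection is that the diagnosis is inferred. Neither document prints an SD at the longer horizon. Linear change doubles the SD only if it holds subject by subject; if only the mean is linear, the SD is undetermined. There is also a second route to the printed limits: an unscaled SD of 0.0970 with n = 23 at 95% gives a half-width of 0.0419 and limits that round to 0.0635 and 0.1473. So a wrong quantile is the probable cause, not a proven one. That much stands. The second route is weaker, because 23 appears nowhere, 60 is in the same sentence, and it doubles the mean but not the SD. It does not rescue the text either, since the interval would then not describe the 60 subjects it is attached to.

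The horizon is inferred as well. SAP 6.2 ties 18 months to the A05 MMSE, not to the A18 scan, and Protocol 7.1.3 lets the scan fall up to 3 months after the final A05 visit. This is a reason to state the horizon; it does not change the arithmetic behind a doubled mean.

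The protocol synopsis plans about 160 subjects, against about 100 in section 8.1.1. At 60% positivity, 160 gives 96 amyloid-positive subjects and, with SD 0.194, a 95% interval of (0.0661, 0.1447), slightly narrower than the printed one. The 16% figure therefore applies to n = 60, and true precision could be better if 160 enrolled. But the sentence under review states 60 and must be right for 60.

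Finally, the impact is small. The planned hypothesis tests compare diagnosis and amyloid groups by ANCOVA (SAP 14.2.1), not this one-sample mean, and SAP section 5 changes the global tau measure to MUBADA, so the exploratory-arm figures may not describe the final primary variable. This limits the weight of the point but does not make the printed label correct.

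**Conclusion.** The concern holds. On the inputs printed in Protocol 8.1.1 and SAP 3.4, the interval (0.0635, 0.1473) is not a 95% confidence interval. It matches a two-sided 90% t interval to four decimals at both limits, and the 95% interval is (0.0553, 0.1555).

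That conclusion uses n = 60, as stated, and an SD of 0.194 at an 18-month horizon, both inferred from the linearity assumption and the numerical match. The narrower statement, that the label does not follow from the stated inputs at n = 60, holds for every SD scaling tried.

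The consequence is modest. The corrected lower limit is still above zero, and no test or decision rule uses the interval. Enrolment is restricted to A05 confirmatory-cohort completers (Protocol 5.3.1: "Subjects who participated as a confirmatory subject in the" A05 study, plus completion of it), so no recruitment target changes. It should still be corrected, because a checkable numerical error stands in both documents as the only planned precision for the main outcome.

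**What to change.** The sponsor should check the source calculation for the SD, n, horizon and confidence level. Then, in both Protocol 8.1.1 and SAP 3.4, do one of the following:
- print the 95% interval as (0.055, 0.156); or
- keep (0.0635, 0.1473) and label it a 90% interval.

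In the same sentence, state the 18-month horizon and the SD of 0.194, so that the interval can be reproduced from the text. If the source calculation turns out to have used other inputs, print those and the interval that follows from them.

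The cost is one sentence in each document, with no added subjects and no change to any analysis.

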8.2. Efficacy Analysis

The tau deposition measured as AV1451 SUVR values change from baseline (CFB) will be summarized by enrolling clinical diagnosis and amyloid status.

Analysis of covariance (ANCOVA) adjusting for baseline AV1451 SUVR and age will be applied to compare the least square (LS) mean SUVR CFB by clinical diagnosis groups, amyloid status and the interaction of two, through proper contrasts set up. The relationship between SUVR CFB and cognitive function assessments CFB will also be explored with ANCOVA models. The analysis details will be provided in statistical analysis plan (SAP).

Clinical and imaging data from the ¹⁸F-AV-1451-A05 study will be made available to the ¹⁸F-AV-1451-A18 study for these analyses once the database lock and unblinding has occurred for ¹⁸F-AV-1451-A05 study.

8.3. Safety Analysis

Safety laboratory test results and vital signs measurements will be summarized by subject and by evaluation time point. Subjects whose laboratory values are outside the pre-determined upper and lower limits of normal will be identified and tabulated.

Adverse events including injection site reactions will be summarized in terms of number and percentage of subjects experiencing an AE. The summary will be further broken down by system organ class (SOC) and preferred term using Medical Dictionary for Regulatory Activities (MedDRA) terms. Adverse events will also be presented by severity, relationship to treatment and seriousness. All subjects who experience SAEs or who discontinue due to AEs will be summarized.

Discontinuation

All subjects who discontinue participation prior to completing the study will be listed and their discontinuation reasons will be tabulated.

Laboratory Data

Subjects whose laboratory values are outside threshold values will be identified and tabulated.

Vital Signs

Vital signs measurements will be summarized by subject and by evaluation time point.

ECG

Any subjects showing QTc > 500 will be highlighted.

8.4. ¹⁸F-AV-1451 Image Analysis

All ¹⁸F-AV-1451 PET images obtained starting at approximately 80 minutes post injection will be analyzed. The ¹⁸F-AV-1451 PET images will be spatially normalized to standard stereotactic atlas space using MNI brain atlas. The uptake in tau protein rich brain regions will be assessed with regions of interest (ROI, designed in MNI brain atlas) in terms for standard uptake value ratio (SUV_r, normalized by cerebellar uptake). The spatially normalized images and the measured SUV_r values will be used to accordingly to accomplish the study objectives.

Exploratory analysis will include co-registration of MRI to the ¹⁸F-AV-1451 PET images for ROI creation and/or partial volume correction of ¹⁸F-AV-1451 PET images using anatomical information from MRI data.

Additional analyses may explore various voxel and threshold based approaches.

9. USE OF DATA AND PUBLICATION

Avid adheres to the Pharmaceutical Research and Manufacturers of America (PhRMA) Principles on Conduct of Clinical Trials and Communication of Clinical Trial Results. A complete copy of these principles is available from Avid and can also be found at the PhRMA website (<http://www.phrma.org>). Our policy is briefly summarized below:

- We commit to timely communication of meaningful results of controlled clinical trials, regardless of outcome.
- As a sponsor, we may recommend that the Investigator(s) delay or decline publication in cases where the study design, conduct, or data are insufficient to allow meaningful interpretation. Avid and the Investigator(s) will discuss the study design and data in advance of the study, and again after completion, and will strive, through appropriate scientific debate, to reach a consensus regarding the potential merits of publication.
- Avid retains the right to review any manuscripts, presentations, or abstracts before they are submitted for publication. Where differences of opinion or interpretation exist regarding data planned for publication, the parties (Avid and the Investigator) should try to resolve them through appropriate scientific debate. Avid retains the right to delay publication for up to 60 days to protect intellectual property.

- Anyone who provides substantial contributions should receive appropriate recognition as an author or contributor when the manuscript is published.

This is a multi-center study. The primary analysis will include data from all centers. A multicenter publication, reporting the primary analysis data set, with authorship from all contributing centers, should precede any other publications.

10. INVESTIGATOR'S REGULATORY OBLIGATIONS

All clinical work conducted under this protocol is subject to Good Clinical Practice regulations; this may include an inspection by Avid and/or Health Authority representatives (FDA, EMA or international regulatory authorities) at any time.

10.1. Institutional Review Board (IRB)

The intent of the research program, the trial protocol, the patient information/informed consent form and any advertising material used to recruit subjects must be submitted to the clinical investigator's local IRB/IEC and its approval must be obtained prior to its use. A copy of the approval must be forwarded to Avid. When necessary, an extension or renewal of IRB/IEC approval must be obtained and also forwarded to Avid.

10.2. Informed Consent

A signed, written informed consent must be obtained from each patient. A copy of the signed informed consent should be given to the patient for their records. A copy of the local IRB/IEC's approved version of the informed consent form must be forwarded to Avid or designee for review prior to being used to obtain patient consent.

10.3. Protocol Adherence

The protocol must be read thoroughly and the instructions must be followed exactly. Where a deviation occurs, it must be documented, the sponsor/monitor informed, and a course of action agreed upon.

10.4. Documents Necessary for Initiation of the Trial

Avid must be provided with the following documents prior to the enrollment of any subjects:

- Original signed and dated Statement of Agreement page;
- Copy of the IRB/IEC and radiation safety committee approval (if applicable);
- Copy of the IRB/IEC stamped approved consent form;
- Name and location of the laboratory utilized for laboratory assays, and other facilities conducting tests, including laboratory certification number and date of certification if available. Avid may be responsible for supplying these to the investigator if a central laboratory is used;

- List of reference range laboratory values. Avid may be responsible for this if a central laboratory is used; and
- Any additional licenses required in order to order to use ¹⁸F-AV-1451.

10.5. Investigational Product Control

The receipt of clinical supplies (i.e. starting material for ¹⁸F-AV-1451) must be documented at the site.

All drug supplies for this trial should be retained in a safe and secure place at all times during the trial. ¹⁸F-AV-1451 Injection should be prepared by a qualified PET manufacturing site and administered by a qualified individual under the investigator's supervision. An up-to-date drug inventory/dispensing record must be maintained. All drug supplies must be accounted for. After completion of the trial, all remaining clinical supplies must be returned to the sponsor or their representative.

10.6. Data Collection

Electronic case report forms (eCRFs) will be used for this trial. Individual patient files should include appropriate source documents, including but not limited to patient's medical records and laboratory test results. The files should include information such as visit dates, records of medical history, examinations administered, laboratory, concomitant treatment, any adverse event encountered and other notes as appropriate. These constitute "source data". All entries on the eCRFs must be backed up by source data. Original electronic versions of imaging studies are also considered source data and should be kept on file by the site/imaging center, and appropriate copies should be forwarded or a designated Imaging Core Lab as specified in the Imaging Manual.

Each patient's source file should include an original signed informed consent form. When the trial is completed, the informed consent form should be kept on file with other trial related records.

All original laboratory reports must be available for review in each patient's file. It is important that the original reports be available for review because of the possibility of inaccuracies or errors in transcribing data from original records to the eCRF.

The eCRFs must be kept in order and up-to-date so that they always reflect the latest observations on the subjects that are enrolled in the trial. The eCRFs must be completed for each patient enrolled in the trial and signed by the investigator. This should be done as soon as possible after completion of the patient's participation in the trial. A monitor will verify the source data for all information on the eCRF.

10.7. Adverse Events

All adverse events encountered during the clinical trial must be documented on the eCRF, whether or not considered drug-related.

Eli Lilly must be notified immediately (as soon as possible, and in all cases within 24 hours) of a drug experience, condition, development, or event, which is considered serious. Eli Lilly must be notified immediately of any findings with the use of the drug

that may suggest significant hazards, contraindications, adverse drug reactions (ADRs) and precautions pertinent to the safety of the drug. The investigator will be requested to complete a separate report form in addition to the information on the CRF. See section 7.7.4 for reporting serious adverse events

If an SAE is determined to be unexpected (not previously reported or described by Avid), and study drug-related, Eli Lilly will notify the investigator in writing. The investigator should forward this notification to the IRB/IEC within 24 hours of receipt.

10.8. Records Retention

All correspondence (e.g., with Avid, IRB/IEC, etc.) relating to this clinical trial should be kept in appropriate file folders. Records of subjects, source documents, and drug inventory sheets pertaining to the trial must be kept on file. Records must be retained until the date a marketing application (NDA) is approved for the drug for the indication for which it is being investigated, or until 3 years following the date of clinical trial termination or completion, whichever is later. If no application is to be filed or if the application is not approved for such indication, records should be kept until 3 years following the date of clinical trial termination or completion.

If an investigator moves, withdraws from an investigation, or retires, the responsibility for maintaining the records may be transferred to another person who will accept the responsibility. Notice of transfer must be made to and agreed upon by Avid.

